5.2 Secondary Objectives

Secondary objectives are to:

1. Compare outcome on XR-NTX versus BUP-NX for the following domains:
 - a. Proportion successfully inducted onto assigned medication.
 - b. Safety, as measured by adverse events and serious adverse events, including opioid overdose episodes, both during the 6-month trial and during the 3-month follow-up period.
 - c. Opioid abstinence, as measured by the Timeline Follow-Back (TLFB) (self-report days using opioids), proportion of opioid-positive urine tests.
 - d. Misuse of alcohol and other drugs of abuse (e.g., cocaine, other stimulants, cannabis, benzodiazepines), by self-report and urine drug screens.
 - e. Tobacco use, as measured by the Fagerström Test for Nicotine Dependence (FTND).
 - f. Craving for opioids, and for other drugs, measured by Visual Analog Scales (VAS).
 - g. Depressive, anxiety, and subacute withdrawal symptoms (typical constellation is fatigue, anorexia, and insomnia), as measured by the Hamilton Depression Scale (17-item) (HAM-D) and the Subjective Opioid Withdrawal Scale (SOWS).
 - h. Problems related to drug abuse, as measured by the Addiction Severity-Index-Lite (ASI-Lite) and EuroQol (EQ-5D).
 - i. HIV risk behavior over time, as measured by the Risk Assessment Battery (RAB).
 - j. Cognitive function, as measured by performance on brief pen and paper tasks (Trail Making Test Parts A and B, Stroop).
2. Explore baseline demographic, clinical, and genetic features as predictors of opioid use outcome over the 6-month trial (main effect of predictors), and as moderators of differential treatment effect (moderator by treatment interaction).
3. Collect a limited dataset to permit analyses of economic costs and benefits of the two treatments.

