10.2 Follow-Up (Phase 4)

An effort will be made to assess all participants at weeks 28 and 36 post randomization. The goals for the follow-up assessments are as follows:

- A. Assess safety in initial weeks and months following discontinuation of XR-NTX or BUP-NX. This would specifically address concerns about overdose deaths after XR-NTX and the criticism leveled at the FDA for approving XR-NTX indication without such data.
- B. Determine 9-month outcome following randomization to up to six months of treatment with XR-NTX or BUP-NX, including rates of relapse after successful completion of 6 months of either XR-NTX or BUP-NX treatment. This would begin to address questions about how long it is necessary to maintain agonist or antagonist treatment and whether there are differences in long-term outcomes; it will address whether early gains are sustained across time; and it will provide descriptive data on the course of opioid use following six months of treatment.
- C. Learn about what interventions are currently available and can be accessed in the community outside of a research study. This would address questions about what is current TAU for opioid dependence.

Aggressive outreach procedures will be implemented to locate and assess participants at the 28 and 36 week follow-up points and to minimize missing data. These procedures are detailed in the study MOP.

This study includes subjects who may be classified as prisoners per 45 CFR 46 Subpart C. If a subject becomes incarcerated during the study, treatment and follow-up procedures may be continued in accordance with local IRB approvals. Procedures must be compliant with 45 CFR 46 Subpart C. Data may be collected either in person, by phone, in writing, and/or by electronic means, provided that data collection follows the procedures approved by OHRP and the local IRB. Details of the nature of the research will not be shared with staff at the jail/prison, and visits, whether in person or by phone, will only be conducted if the participant's confidentiality can be maintained and no audio-taping occurs.

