5.3.3 Primary Outcome Analysis Methods

Since the results of the interim analysis indicated a differential treatment initiation rate assessment, the data analysis modification will be employed. As noted in Section 3.2, if there is a differential treatment initiation rate in the early randomizers group, an interaction term for the treatment by randomization timing variables will be incorporated into the final analysis model.

Data will be analyzed using a Cox proportional hazards model. The model is as follows:

$$\log h(t | CUF) = \log h_0(t | CUF) + \beta_1 * Treatment + \beta_2 * TIMING + \beta_3 * CTP + \beta_4 * STRATA + \beta_5 * Treatment * TIMING$$

where h is the hazard rate, roughly defined as the probability per time unit that a case that has not relapsed to the beginning of the respective interval will relapse in that interval. Conceptually, it can be thought of as the number of relapse per time units in the respective interval, divided by the average number of non-relapse cases at the mid-point of the interval. The quantity h0 is an arbitrary baseline hazard rate.

The SAS PHREG procedure will perform survival analysis based on the Cox model to estimate the hazard ratio for the treatments. The 95% Wald Confidence limits will be estimated.

The following SAS Code will be used to analyze the data:

```
PROC PHREG;
    CLASS TREATMENT (REF='BUP-NX') TIMING (REF='Late');
    MODEL TIME*STATUS = TREATMENT TIMING CTP STRATA
    TREATMENT*TIMING;
    HAZARDRATIO TREATMENT;
RUN;
```

The variables included in the SAS code are described as follows:

- TREATMENT- This variable defines the randomized treatment assignment. (BUP-NX or XR-NTX)
- TIME- Time to relapse
- STATUS- Censoring variable
- CTP- CTP
- STRATA- Randomization Stratification factor pertaining to the baseline opioid severity level classified as <6 bags (Low Severity) or ≥ 6 bags (High Severity).
- TIMING- Binary baseline variable (early vs. later randomization as noted in Section 5.1 defined as either 'Late' or 'Early').

The initial analysis will be the construction of the asymptotic 95% CI for the hazard ratio of the difference between the treatment arms in the time to event distribution for the primary outcome. The study arm success rates with confidence intervals at week 24 and the difference in success rate at that time point and associated confidence intervals will be constructed.

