Adverse events (AEs), including serious adverse events (SAEs), will be summarized by body system and preferred term using MedDRA (The Medical Dictionary for Regulatory Activities) version 19.0 or higher. Adverse events will be presented in two ways: (1) the number and proportion of participants experiencing at least one incidence of each event will be presented overall and by treatment group. The incidence of adverse events and serious adverse events by

type will be compared between treatment arms using either Fisher's Exact mid-p-value or Chi-Square analysis as appropriate; and (2) a table displaying the total number of each event will be given overall and by treatment group. Listings of serious adverse events will be given, sorted by treatment, body system and preferred term. Detail in these listings will include severity, relationship to study drug, and action taken as available.

Treatment emergent AEs are defined as AEs occurring after participants have been inducted on study medication. Induction is defined as having had an injection if in the XR-NTX arm or having been dispensed medication if in the BUP-NX arm.

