Formication			
Facial paresis			
Burning sensation			
Sedation			
Sciatica			
Ageusia			
Loss of consciousness			
Infections and infestations			
Bronchitis			
Upper respiratory tract infection			
Cellulitis			
Influenza			
Abscess limb			
Pneumonia			
Urinary tract infection			
Sinusitis			
Gastroenteritis			
Eye infection			
Bursitis infective			

Table 35: Summary of Treatment Emergent* MedDRA Coded Adverse Events by Treatment Arm			
System Organ Class/ Preferred Term (MedDRA v19.0 or higher)	BUP-NX (N=)	XR-NTX (N=)	Total (N=)
Aspergilloma			
Acarodermatitis			
Tooth abscess			
Subcutaneous abscess			
Abscess neck			
Nasopharyngitis			
Muscle abscess			
Lung infection			
Kidney infection			
Injection site abscess			
Hepatitis viral			
Groin abscess			
Gingival abscess			
Gastroenteritis viral			
Injury, poisoning and procedural complications			
Overdose			
Laceration			
Contusion			
Limb injury			
Ligament sprain			
Eye contusion			
Muscle strain			
Joint injury			
Joint dislocation			
Head injury			
Tooth injury			
Tooth fracture			
Burns third degree			
Tendon injury			
Skin abrasion			
Road traffic accident			
Periorbital haematoma			
Nerve injury			
Multiple fractures			
Lower limb fracture			
Avulsion fracture			
Limb crushing injury			

Table 35: Summary of Treatment Emergent* MedDRA Coded Adverse Events by Treatment Arm			
System Organ Class/ Preferred Term (MedDRA v19.0 or higher)	BUP-NX (N=)	XR-NTX (N=)	Total (N=)
Musculoskeletal and connective tissue disorders			
Back pain			
Arthralgia			
Myalgia			
Joint swelling			
Neck pain			
Musculoskeletal pain			
Pain in extremity			
Muscle contracture			
Arthritis			
Temporomandibular joint syndrome			
General disorders and administration site conditions			
Chest pain			
Peripheral swelling			
Oedema peripheral			
Fatigue			
Drug withdrawal syndrome			
Chills			
Asthenia			
Pyrexia			
Pain			
Local swelling			
Feeling jittery			
Investigations			
Transaminases increased			
Hepatic enzyme increased			
White blood cell count decreased			
Liver function test increased			
Blood urine present			
Skin and subcutaneous tissue disorders			
Hyperhidrosis			
Rash			
Pruritus			
Urticaria			
Ecchymosis			
Cold sweat			
Alopecia			
Acne			

Table 35: Summary of Treatment Emergent* MedDRA Coded Adverse Events by Treatment Arm			
System Organ Class/ Preferred Term (MedDRA v19.0 or higher)	BUP-NX (N=)	XR-NTX (N=)	Total (N=)
Respiratory, thoracic and mediastinal disorders			
Oropharyngeal pain			
Cough			

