Rhinorrhoea			
Epistaxis			
Throat tightness			
Sinus congestion			
Respiratory depression			
Nasal congestion			
Asthma			
Eye disorders			
Vision blurred			
Eye irritation			
Dry eye			
Diplopia			
Amaurosis fugax			
Metabolism and nutrition disorders			
Decreased appetite			
Dehydration			
Hyponatraemia			
Hypokalaemia			
Gout			
Vascular disorders			
Hot flush			
Hypertension			
Renal and urinary disorders			
Nephrolithiasis			
Urinary retention			
Pollakiuria			
Haematuria			
Dysuria			

Table 35: Summary of Treatment Emergent* MedDRA Coded Adverse Events by Treatment Arm			
System Organ Class/ Preferred Term (MedDRA v19.0 or higher)	BUP-NX (N=)	XR-NTX (N=)	Total (N=)
Reproductive system and breast disorders			
Vaginal discharge			
Menstruation delayed			
Breast mass			
Breast discharge			
Hepatobiliary disorders			
Hepatic failure			
Cholecystitis			
Surgical and medical procedures			
Tooth extraction			
Cardiac disorders			
Tachycardia			
Social circumstances			
Victim of crime			
Product issues			
Device deployment issue			
Pregnancy, puerperium and perinatal conditions			
Ectopic pregnancy			

*Note: treatment emergence is defined as any adverse events that occurred after the study day of induction for those participants inducted onto study medication.

Table 36: Summary of Treatment Emergent* MedDRA Coded Serious Adverse Events by Treatment Arm			
System Organ Class/ Preferred Term (MedDRA v19.0 or higher)	BUP-NX (N=)	XR-NTX (N=)	Total (N=)
Participants with at least one treatment emergent serious adverse event			
Psychiatric disorders			
Suicidal ideation			
Suicide attempt			
Self injurious behavior			
Psychotic disorder			
Depression suicidal			
Depression			
Delirium			
Anxiety			
Affective disorder			
Injury, poisoning and procedural complications			
Overdose			
Multiple fractures			
Burns third degree			
Infections and infestations			
Cellulitis			
Abscess limb			
Pneumonia			
Influenza			
Groin abscess			
Gastroenteritis			
Bronchitis			
Nervous system disorders			
Syncope			
Seizure			
Facial paresis			
Respiratory, thoracic and mediastinal disorders			
Respiratory depression			
Asthma			
Musculoskeletal and connective tissue disorders			
Back pain			
Metabolism and nutrition disorders			
Dehydration			
Hepatobiliary disorders			
Hepatic failure			

Table 36: Summary of Treatment Emergent* MedDRA Coded Serious Adverse Events by Treatment Arm			
System Organ Class/ Preferred Term (MedDRA v19.0 or higher)	BUP-NX (N=)	XR-NTX (N=)	Total (N=)

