General disorders and administration site conditions			
Chest pain			
Gastrointestinal disorders			
Vomiting			
Eye disorders			
Diplopia			
Pregnancy, puerperium and perinatal conditions			
Ectopic pregnancy			

*Note: treatment emergence is defined as any adverse events that occurred after the study day of induction for those participants inducted onto study medication.

Table 37: Listing of Treatment Emergent* Adverse Events by Treatment Arm [Serious Adverse Events Noted in Grey] Treatment Arm = BUP-NX										
									MedDRA	
CTP	Participant ID	AE Description	Onset date	Severity of AE	Relatedness	Outcome	Resolution Date	AE Associated With	Preferred Term	System Organ Class

Note: MedDRA v19.0 or higher.

*Note: treatment emergence is defined as any adverse events that occurred after the study day of induction for those participants inducted onto study medication.

Table 38: Listing of Non-Treatment Emergent Adverse Events in Randomized Participants by Treatment Arm
[Serious Adverse Events Noted in Grey]
Treatment Arm = BUP-NX

									MedDRA	
CTP	Participant ID	AE Description	Onset date	Severity of AE	Relatedness	Outcome	Resolution Date	AE Associated With	Preferred Term	System Organ Class

Note: MedDRA v19.0 or higher.

*Note: treatment emergence is defined as any adverse events that occurred after the study day of induction for those participants inducted onto study medication.

Table 38: Listing of Non-Treatment Emergent Adverse Events in Randomized Participants by Treatment Arm
[Serious Adverse Events Noted in Grey]
Treatment Arm = XR-NTX

									MedDRA	
CTP	Participant ID	AE Description	Onset date	Severity of AE	Relatedness	Outcome	Resolution Date	AE Associated With	Preferred Term	System Organ Class

Note: MedDRA v19.0 or higher.

*Note: treatment emergence is defined as any adverse events that occurred after the study day of induction for those participants inducted onto study medication.

Table 39: Listing of Non-Treatment Emergent Adverse Events Among Screen Failures
[Serious Adverse Events noted in Grey]

									MedDRA	
CTP	Participant ID	AE Description	Onset date	Severity of AE	Relatedness	Outcome	Resolution Date	AE Associated With	Preferred Term	System Organ Class

Note: MedDRA v19.0 or higher.

SAE Narratives

Table 40: Listing of Serious Adverse Events by Treatment Arm										
Treatment Arm = BUP-NX										
									MedDRA	

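### The only planned by-arm overdose counts (SAP Tables 35 and 36) cover inducted participants and pool all time after induction, so they show neither of the two periods in objective 1b and do not compare the randomized groups

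*SAP*

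**What the plan says.** **What is promised.** Protocol section 5.2, objective 1b, compares the arms on adverse and serious adverse events, "including opioid overdose episodes, both during the 6-month trial and during the 3-month follow-up period". Goal A of protocol section 10.2 is safety after study medication stops: "This would specifically address concerns about overdose deaths after XR-NTX".

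**What is summarized.** SAP section 7.4.1 records any reported overdose as an AE or SAE. It plans counts and proportions by preferred term, overall and by arm, with a between-arm test by event type. It then adds: "Treatment emergent AEs are defined as AEs occurring after participants have been inducted on study medication". The shells in SAP Appendix A carry an overdose row in two places, Table 35 ("Summary of Treatment Emergent* MedDRA Coded Adverse Events by Treatment Arm") and Table 36 ("Summary of Treatment Emergent* MedDRA Coded Serious Adverse Events by Treatment Arm"). The footnote to Table 35, which Table 36 repeats, reads: "treatment emergence is defined as any adverse events that occurred after the study day of induction for those participants inducted onto study medication".

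**What is listed.** Events outside that definition go to Table 38, "Listing of Non-Treatment Emergent Adverse Events in Randomized Participants by Treatment Arm". Serious events and deaths are also listed by arm in Tables 40 and 41.

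**What is known about induction.** SAP section 5.3.3 states: "Since the results of the interim analysis indicated a differential treatment initiation rate assessment, the data analysis modification will be employed".

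**The concern.** Two features of Tables 35 and 36 work against the stated objective.

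1. **Period.** The counts start after induction and have no end. An overdose in week 3 and one in week 33 fall in the same cell. Objective 1b names two periods, and goal A is about time after stopping; neither can be read from a pooled count.
2. **Population.** Induction happens after randomization. XR-NTX requires completed detoxification and BUP-NX does not, and the interim assessment found that initiation differed. A count confined to inducted participants therefore selects differently in the two arms.

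The protocol's introduction (section 4.1) cites the criticism that the pivotal XR-NTX trial did not adequately assess overdose after treatment. With these shells alone, the trial would have no pre-specified by-arm summary of that outcome, and any split would be made after the results were known.

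**Working it through.** **Step 1. Check every safety output that could hold an overdose or a death (SAP Appendix A).**

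| Output | Population | Time | By-arm overdose count? |
|---|---|---|---|
| Table 4, reason for early termination | Randomized | To week 36, not split | No; all-cause death row |
| Table 8, reason for stopping medication | Inducted | Not split | No; all-cause death row |
| Tables 33, 34 | Inducted | After induction, no end | No; Table 34 has an all-cause death row |
| Tables 35, 36 | Inducted | After induction, no end | Yes |
| Tables 37, 38, 40, 41 | Listings; 38, 40 and 41 reach never-inducted participants | Onset date only | No counts or denominators; no study day or last-dose date |

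No shell gives overdose by arm for all randomized participants, and none divides it at week 24 or at last dose.

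**Step 2. Size of the pooled follow-up.** The week 24 target is day 167 and the week 36 target is day 251 (protocol Table 3). Days 0-167 are 168 days; days 168-251 are 84. Follow-up share = 84 / (168 + 84) = 1/3 of scheduled time.

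**Step 3. Planning values for induction.** SAP section 3.2 states more than 80% power for a difference of .25 when the BUP-NX rate is .85, so .85 versus .60. With 50 per arm (assumed from 100 early randomizers) and a pooled normal test:

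- standard error under the null: √(2 × .725 × .275 / 50) = .0893
- standard error under the alternative: √(.85 × .15 / 50 + .60 × .40 / 50) = .0857
- z = (.25 − 1.96 × .0893) / .0857 = .87, so power is 81%

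The stated figure reproduces, so .85 and .60 are taken as the planning values.

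**Step 4. Early randomizers left out at those values.** SAP section 3.3 projects about 250 early randomizers; assume 125 per arm.

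- BUP-NX: 125 × (1 − .85) = 18.75, about 19
- XR-NTX: 125 × (1 − .60) = 50

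The .25 is a difference the rule was built to detect, not an observed or forecast one.

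**Step 5. What a significant interim result guarantees.** SAP section 5.2.2 uses a two-sided Fisher exact test at 0.05. The smallest significant gaps with 50 per arm are:

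| Inducted, BUP-NX | Inducted, XR-NTX | Gap | p |
|---|---|---|---|
| 50 | 44 | 6 | 0.027 |
| 45 | 36 | 9 | 0.040 |
| 43 | 33 | 10 | 0.034 |
| 42 | 32 | 10 | 0.039 |

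If BUP-NX induction was 84% to 100%, and the difference ran in the anticipated direction, the result implies at least 6 to 10 more non-inducted XR-NTX participants among those first 100, as of that assessment. It required only 21 days of opportunity (SAP section 5.2), while induction stays open to week 22, so some may have been inducted later.

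**Step 6. When does adverse event collection end?** Protocol Appendix A runs follow-up to 30 days after the last study visit. Appendix B (2.0 A) ends assessment 30 days after the last active treatment visit, yet also has events assessed at each clinic visit during the study. Active questioning is tied to medical management visits (protocol section 11.2.7), which end by week 24 or at relapse (section 11.3.2). Under Appendix B's end date, most of the follow-up period would be uncovered.

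**The case against.** The strongest reply is that nothing is hidden. The prose of SAP section 7.4.1, like protocol section 12.10, describes summaries by arm without confining them to treatment-emergent events; the restriction comes from the shells. A table with no end date covers both periods, and objective 1b does not say that they must be tabulated separately. Overdoses should be few, and dated listings by arm plus SAE narratives let a reader place each one. Table 4 also counts all-cause deaths by arm among randomized participants.

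Much of this stands. A reader might infer that the SAP excludes never-inducted participants by rule, or that their overdoses go unreported. Neither is so: the prose is broader than the shells, and Tables 38, 40 and 41 reach those participants. What does not stand is that listings meet the objective. They have no denominators, study day or last-dose date, and a hand count made once results are known is not a pre-specified comparison. Even the broader reading of 7.4.1 sets no period. The death rows in Tables 4, 8 and 34 give neither an overdose cause nor a study period.

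A reader might also scale the interim gap up to all early randomizers and call the result a minimum. The documents do not support that: the gap is a sample result on 100 people, later participants may differ, and the induction window was still open.

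**Conclusion.** The concern holds for the outputs as specified. Tables 35 and 36 are the only by-arm overdose counts among the shells. They cannot show the trial and follow-up periods separately, and they condition on a post-randomization event already reported to differ by arm.

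The size is uncertain. About 19 BUP-NX and 50 XR-NTX early randomizers would be left out at the planning rates with 125 per arm; the interim result alone guarantees only a gap of 6 to 10 among the first 100, with 50 per arm and BUP-NX induction of at least 84%. The documents give no observed induction rates, and nothing on late randomizers' non-induction.

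Two stronger conclusions might be drawn and should not be. One is that the tables favour a particular arm: the documents give no overdose rate for never-inducted participants, so the direction is unknown. The other is that only the outputs need attention because collection is secure: the two protocol appendices disagree on when collection ends. This is a gap worth closing at low cost; it does not touch the primary analysis.

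**What to change.** 1. Add to SAP section 7.4.1 a descriptive overdose table by arm for all randomized participants: fatal and non-fatal, participants and events, exact confidence intervals, no test. Split it at day 0-167 and day 168 to the week 36 visit. Beside the follow-up columns show how many per arm attended weeks 28 and 36.
2. Add study day and days since last study dose to Tables 37, 38, 40 and 41.
3. State that adverse event collection runs to 30 days after the last study visit, as in protocol Appendix A, and correct Appendix B to match.
4. Keep Tables 35 and 36 as they are.

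Optionally, add a split into time on and off study medication, labelled as non-randomized. Its XR-NTX window must be fixed in advance, because the documents support both about 28 days (prescribing information, section 5.1) and 5 weeks (protocol section 8.5.1.3).

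**Cost.** One small table, two listing columns and a sentence in each document, all from event dates, injection dates and the BUP-NX dose log. Cells will be small. Ascertainment will be thinner after relapse, when weekly visits stop, and in follow-up; the attendance figures are there to make that visible.
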